1 INTRODUCTION

This statistical analysis plan (SAP) reflects detailed statistical methods to be used for studying Montelukast on Gastrointestinal Tolerability in patients with Relapsing Forms of Multiple Sclerosis receiving Tecfidera[®] (Dimethyl Fumarate) Delayed-Release Capsules. The SAP is based on the final version of protocol 109MS414 (Version 3) dated 01 February 2016.

2 STUDY OBJECTIVES AND ENDPOINTS

2.1 Primary Objective and Endpoint

The primary objective of this study is to evaluate whether Montelukast can reduce the severity of gastrointestinal (GI) events, measured by the Gastrointestinal Symptom Rating Scale (GSRS), after oral administration of Dimethyl Fumarate (DMF) in subjects with relapsing forms of multiple sclerosis (MS).

The primary endpoint of this study is the proportion of subjects with a worsening in the severity of GI adverse events (AEs), measured by the average change from Day 0 to Day 10 in GSRS score. If a patient takes the randomized study treatment one day after his or her GSRS score reaches the GI threshold, Day 0 is defined as the day prior to the first dose of randomized study treatment. If a patient takes the randomized study treatment on the same day when the GSRS score reaches the GI threshold, Day 0 is defined as the day with the first dose of randomized study treatment. If a patient missed the randomized study treatment for a few days after the GSRS score reached the GI threshold, Day 0 is the day immediately prior to the first dose when the GI threshold was reached. Day 10 is defined as 10 days after Day 0.

2.2 Secondary Objectives and Endpoints

[figure not shown]
The secondary objectives in this study population are:

- To evaluate whether Montelukast after oral administration of DMF in subjects with relapsing forms of MS:
 - decreases discontinuations due to GI events
 - reduces the number of subjects taking symptomatic therapies for GI events
- To investigate the effect of Montelukast on the incidence of flushing events after oral administration of 240 mg DMF in subjects with relapsing forms of MS

The secondary endpoints are:

- Average change of GI severity scores from Day 0 to Day 10, as measured by the total change of GSRS scores from Day 0 over the first 10 days (Day 1 to Day 10), divided by the total number of days with GSRS recorded
- Average change of GI severity scores from Day 0 to Week 10, as measured by the total change of GSRS score from Day 0 over the first 10 weeks (Day 1 to Week 10), divided by the total number of days with GSRS recorded

- Time to first worsening of GSRS in GI severity
- Time to recovery to Day 0 GSRS score from the last occurrence of the worst score in GI severity
- Average change of GSRS score from Day 0 score to Weeks 1, 2, 3, 4, 5, 6, and 8
- Average change of GSRS score from Day 0 to 72 hours from the initiation of randomized study treatment
- Proportion of subjects who require GI symptomatic therapy during the study
- Percentage of subjects who discontinue DMF therapy due to GI-related AEs from Day 0 to Week 10
- Proportion of subjects who experience flushing events

2.3 Exploratory Objectives and Endpoints

3 STUDY DESIGN

3.1 Study Overview

This multicenter study will evaluate the effect of Montelukast on GI tolerability with relapsing forms of MS treated with DMF at approximately 50 study sites in the US. It is expected that approximately 295 subjects will be initially randomized to obtain approximately 118 subjects dosed with randomized study treatment (59 subjects dosed with randomized study treatment (59 subjects will be eligible to be dosed with randomized study treatment. Randomized subjects will be required to reach a predefined threshold of GI symptom severity before dosing with randomized study treatment is initiated. Subjects who withdraw from the study after initiating randomized study treatment will not be replaced.

Subjects will enter a 2-week (+14 days) Screening Period and record pertinent information regarding GI-related events to allow characterization of background GIrelated events using the electronic diary (eDiary). Subjects will be required to be \geq 75% compliant in the 14 days prior to randomization to remain eligible to participate in the study. Subsequently, eligible subjects will initially take DMF (120 mg twice daily orally for the first week, 240 mg twice daily orally thereafter) for up to 28 days (DMF-GI Monitoring Period) and record GI-related events in the eDiary. During this period, subjects will take DMF, GSRS scores will be monitored, and subjects who reach a specific threshold will receive an alert through the eDiary to start taking randomized study treatment (10 mg once daily Montelukast or placebo) the same day in accordance with the prescribing and labeling information. Subjects who do not meet the threshold or do not demonstrate \geq 75% compliance with the eDiary in the 14 days prior to randomization will be discontinued. Subjects will also use the eDiary to record DMF dosing, randomized study medication dosing, and any symptomatic concomitant medications/procedures. Eligible subjects will return to the study site at Weeks 0, 2, 4, 8 (±2 days) and Week 10 (±3 days) for evaluation by study site staff. If more convenient for the subject, visits at Weeks 2 and 8 may be performed remotely by a contracted home health nurse. The Safety Follow-Up Telephone Interview will be conducted 2 weeks (±5 days) after the Week 10 study visit or date of the Early Termination (ET) Visit.

The dose of DMF used will be as described in the USPI. Subjects will take DMF for up to 14 weeks, including 8 weeks with the concomitant randomized study treatment (Montelukast or placebo), and will record pertinent information regarding GI-related events in an eDiary.

Information on AEs and SAEs will be collected for possible correlation with GI-related events. For the purposes of this study, relapses of MS will not be considered AEs, and data related to relapses will be captured only if the event is deemed an SAE or results in a subject's discontinuation. Relapses of MS resulting in hospitalization are considered SAEs and will be reported to the FDA. However, they will not be reported as SAEs in the study unless the relapse is complicated by other SAEs or is fatal.

[figure not shown]

Figure 1: Study Design

Abbreviations: BID = twice daily; DMF = dimethyl fumarate; GI = gastrointestinal; QD = once daily. *Use of symptomatic therapies, as specified in Protocol Section 10.3.2, is permitted from Day 10 onward.

3.1 Definition of the GSRS threshold

Two definitions of the GSRS threshold were used in this study.

Definition in the version 1 of the protocol: GSRS score of ≥ 5 in one question for 1 day or a GSRS score of ≥ 4 in one question for 2 consecutive days or GSRS score of ≥ 3 in one question for 3 consecutive days.

Definition in the 2^{nd} and higher Protocol versions: GSRS score of ≥ 3 in one question for 1 day or a GSRS score of ≥ 2 in one question for 2 consecutive days.

3.2 Overall Study Duration and Follow-Up

The study period consists of a 2-week (+14 days) Screening Period, up to a total of 14 weeks of DMF therapy (including DMF-GI Monitoring Period and randomized treatment administration period), including 8 weeks of concomitant randomized study treatment (DMF + Montelukast or DMF + placebo), and the Safety Follow-Up Telephone Interview. The duration of a subject's participation will be up to 18 weeks. Subjects who discontinue the study early will complete the same assessments specified for the Week 10 Visit.

4 SCHEDULE OF EVENTS

Table 1 includes details on the schedule of activities in Study 109MS414.

Table 1:Schedule of Activities

Assessment	Screening Visit ^a	Screening Period (2 weeks +14 days)	Randomization Visit ^a ^{(Week -4})	DMF-GI Monitoring Period (up to 28 days)	Wk 0 ^{a,b}	Wk 2 ^c	Wk 4 ^a	Wk 8 ^c	Wk 10 ^a /ET	Safety Follow-Up ^d (± 5 days)
Clinic Visit	Х		X		Х	Х	Х	Х	Х	
Informed Consent	Х									
Eligibility Criteria	Х		X ^e							
Demographics	Х									
Vital signs ^f	Х									
Medical History (incl. MS disease status) ^g	Х									
Alcohol Consumption	Х									
Tobacco Use	Х									
Pregnancy Testing ^h	Х		Х							
Concomitant Medications/ Procedures	X		Х		Х	Х	Х	Х	X	Х
			1	1			1			
Blood Biomarkers (optional) ^j			X				Х		Х	

Assessment	Screening Visit ^a	Screening Period (2 weeks +14 days)	Randomization Visit ^a ^{(Week -4})	DMF-GI Monitoring Period (up to 28 days)	Wk 0 ^{a,b}	Wk 2 ^c	Wk 4 ^a	Wk 8 ^c	Wk 10ª/ET	Safety Follow-Up ^d (± 5 days)
Dispense eDiary	Х									
eDiary Training	Х									
eDiary Entries (Daily) ^k										
Return eDiary to Clinical ¹			X ^m	X ^m					X	
Dispense DMF With Dosing Instructions			Х							
DMF Administration (Daily)			DMF administration will occur every day as per the USPI							
Randomization			Х							
Dispense Randomized Study Treatments			X ⁿ							
Randomized Study Treatment Administration (Daily)					Randomized study treatment administration will occur every day as per the prescribing information.					
SAEs	SAE data will be collected from the signing of the informed consent up to the Safety Follow-Up Telephone Interview. MS relapses resulting in hospitalization considered SAEs but will not be reported as SAEs in the study unless the relapse is complicated by other SAEs or is fatal.									
AEs		AE data will be collected from the first dose of DMF up to the Safety Follow-Up Telephone Interview.								

Note: Weeks 2, 4, and 8 will have a visit window of ± 2 days, and Week 10 will have a visit window of ± 3 days.

Abbreviations: AE = adverse event; DMF = dimethyl fumarate; DNA = deoxyribonucleic acid; eDiary = electronic diary; EDSS = Expanded Disability Status Scale; ET = early termination; GI = gastrointestinal; GSRS = Gastrointestinal Symptom Rating Scale; sclerosis: RNA = ribonucleic acid; SAE = serious adverse event; USPI = United States Prescribing Information; Wk = week.

^a This visit must be performed in clinic.

^b Subjects will receive an alert through the eDiary if their GSRS scores reach the appropriate threshold. This alert will tell the subject to begin taking the randomized study treatment the same day. At this time, study site should arrange the Week 0 Visit as soon as possible after the first administration of randomized study treatment. Visit dates will be measured from the first administration of randomized study treatment.

^c This visit may be performed remotely if more convenient for the subject; site must telephone the subject to document concomitant medications/procedures and AEs.

^d The safety follow-up will be performed as a telephone interview.

^e GI symptom and eDiary compliance assessment.

^f Including height and weight measurements and vital signs (temperature, blood pressure, and sitting blood pressure).

- ^g Medical history, including MS disease status, will include collection of information on duration of MS, relapse history, EDSS score, and treatment for MS.
- ^h Dipstick test (only for women of childbearing potential).

^j Serum, RNA, and DNA samples will be collected for biomarker analysis and future use analysis in subjects who provide additional consent. A single DNA sample can be taken at any of prespecified timepoints.

^k Subjects will be required to record their daily GI symptoms in the eDiary every day from the Screening Visit up to Week 10.

¹ eDiaries will be returned if (1) the subject fails during the Screening Period, (2) the subject does not reach the required GI symptom threshold during the DMF-GI Monitoring Period, or (3) the subject completes or discontinues the study.

^m Subjects who do not reach the GI symptom threshold during the DMF-GI Monitoring Period (a GSRS score of ≥ 5 in 1 question for 1 day, ≥ 4 in 1 question for 2 consecutive days, or ≥ 3 in 1 question for 3 consecutive days) will be discontinued.

ⁿ Subjects are dispensed randomized study treatment at this visit but must not begin taking the medication until alerted about their eDiary.

5 INTERIM ANALYSIS

No interim analysis will be performed. The study will be stopped for administrative reasons. Enrollment will be closed when approximately 60 patients are randomized and dosed up to Day 10. Enrolled patients will be followed until they complete the safety follow up visit. Results will be reviewed at the group level when these patients complete the study up to Day 10, and at the subject level when these patients complete the whole study.

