Change from Day 0 to Day 10 in GSRS rating will be computed. The proportion of subjects with worsening, defined as increase in GSRS rating in GI AEs, will be estimated to obtain the rate of worsening in the 2 arms. The difference in the rate of worsening in GI AEs will be analyzed using a chi-square test and the logistic regression model adjusting for covariates and confounding factors.

Secondary Endpoints Analysis

The average change of GI severity score from Day 0 to Week 10 will be analyzed using an analysis of covariance (ANCOVA) model to adjust for covariates and confounding factors such as early drop-outs. Time to first worsening and time to recovery from the last worst GSRS score to Day 0 GSRS score will be analyzed using Kaplan-Meier methods and a Cox proportional hazards model. The average change

CONFIDENTIAL

The information contained herein may not be used, disclosed, or published without the written consent of Biogen MA Inc.

Safety:

Statistical Methods:

of GSRS score from Day 0 score at various timepoints will be analyzed using an ANCOVA model adjusting for covariates and confounding factors.

The proportion of subjects who require GI symptomatic therapy during the study period will be compared using the chi-square test. The percentage of subjects who discontinue DMF therapy due to GI-related events from the Randomization Visit to Week 10 will be summarized by treatment arm. The proportion of subjects who experience flushing events in each treatment group will also be summarized.

Exploratory Endpoints Analysis

No interim analysis will be performed.

Interim Analysis:

Sample Size Determination: Assuming t

[figure not shown]
Assuming that 40% of the placebo subjects will be improving (by chance) without any intervention, a total sample size of 118 (dosed with randomized study treatment), 59 per treatment arm (after randomization), would provide approximately 80% power to detect a 30% difference between the treatment arm and placebo arm in proportion of subjects with any improvement in GI severity, as measured by the average change from Day 0 in GSRS score to Day 10, including an early discontinuation of 15%.

Version 3

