16.7. Sample Size Considerations

Assuming that 40% of the placebo subjects will be improving (by chance) without any intervention, a total sample size of 118, 59 per treatment arm (dosed with randomized study treatment), would provide approximately 80% power to detect a 30% difference between the treatment arm and placebo arm in proportion of subjects with any improvement in GI severity, as measured by the average change from Day 0 in GSRS score to Day 10, including an early discontinuation of 15%.

CONFIDENTIAL

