6 SAMPLE SIZE JUSTIFICATION

Assuming that 40% of the placebo subjects will be improving (by chance) without any intervention, a total sample size of 118 (dosed with randomized study treatment), 59 per treatment arm (after randomization), would provide approximately 80% power to detect a 30% difference between the treatment arm and placebo arm in proportion of subjects with any improvement in GI severity, as measured by the average change from Day 0 in GSRS score to Day 10. Power was estimated assuming a 15% early discontinuation rate.

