7.1 Analysis population

7.1.1 Modified ITT population

The modified intent-to-treat (modified ITT) population consists of all patients who were randomized, received at least one dose of DMF treatment, received at least one dose of study treatment (Montelukast or placebo) on/after the first DMF dose date, and had at least one GSRS score measurement during the Day 1 - Day 10 period.

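### The SAP closes enrolment at about 60 dosed patients but still carries 118 dosed and about 80% power, and gives no power for the reduced size

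*Combined protocol and SAP*

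**What the plan says.** SAP 5 says that there will be no interim analysis, that the study will stop for administrative reasons, and that "Enrollment will be closed when approximately 60 patients are randomized and dosed up to Day 10". It adds: "Enrolled patients will be followed until they complete the safety follow up visit".

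Two other parts of the same SAP keep the earlier size. SAP 3.1 (Study Overview) says: "It is expected that approximately 295 subjects will be initially randomized to obtain approximately 118 subjects dosed with randomized study treatment". SAP 6 says that "a total sample size of 118 (dosed with randomized study treatment), 59 per treatment arm (after randomization), would provide approximately 80% power" for a 30-point difference from a 40% placebo improvement rate, and that "Power was estimated assuming a 15% early discontinuation rate". Protocol section 3 (Synopsis) and section 16.7 give the same size and power: "59 per treatment arm (after randomization), would provide approximately 80% power to detect a 30% difference" and "a total sample size of 118, 59 per treatment arm (dosed with randomized study treatment), would provide approximately 80% power".

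SAP 6 does not mention the closure and does not label 118 as a superseded target. Neither document gives power, precision or a detectable difference for about 60 patients, or says how many patients are expected in the final analysis.

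**The concern.** About 60 patients is roughly half of 118. The SAP keeps a two-sided 5% test and a primary P-value (SAP 7 and 7.3.3), so power still bears on how the result is read: a non-significant result means less at 55% to 67% power than at 80%. Someone who goes to SAP 6 for the trial's power finds about 80%, attached to a size that SAP 5 does not commit to reaching. SAP 3.1 is also worded as a present expectation, so the document states two sizes without reconciling them.

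**Working it through.** **Inputs.** Improvement 40% on placebo against 70% on montelukast (SAP 6, reading the 30% difference as absolute); two-sided 5% (SAP 7); 1:1 allocation (protocol 9.2); 59 dosed per arm and 15% early discontinuation (SAP 6); about 60 in total at closure (SAP 5), taken as 30 per arm. SAP 6 is framed as improvement and the primary endpoint as worsening. If unchanged scores are ignored, the mirror image (60% against 30% worsening) gives the same power.

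**Step 1: reproduce the SAP's own figure.** The mean rate is 0.55, so 2 × 0.55 × 0.45 = 0.495, and 0.4 × 0.6 + 0.7 × 0.3 = 0.45.

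- Uncorrected size for 80% power: (1.960 × √0.495 + 0.842 × √0.45)² / 0.30² = 41.97, so 42 per arm.
- Continuity-corrected: (41.97/4) × [1 + √(1 + 4/(41.97 × 0.30))]² = 48.4, so 49 per arm.
- With 15% loss: 49/0.85 = 57.6, so 58 per arm and 116 in total, against 118 stated. The uncorrected 42 gives 42/0.85 = 49.4, so 50 per arm and 100 in total, which does not match.

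Continuity-corrected power at n per arm is Φ{[0.30 − 1/n − 1.960 × √(0.495/n)] / √(0.45/n)}. The SAP's evaluable number is 59 × 0.85 = 50.2. At n = 50: (0.300 − 0.020 − 0.195)/0.0949 = 0.896, and Φ(0.896) = 81.5%. The SAP's figure reproduces. The SAP does not state its method; this is the one that fits.

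**Step 2: the same formula at 30 evaluable per arm.** (0.3000 − 0.0333 − 0.2518)/0.1225 = 0.122, and Φ(0.122) = 54.8%. Without the 1/n correction: 0.0482/0.1225 = 0.394, and Φ(0.394) = 65.3%.

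**Step 3: four methods side by side.** Fisher and likelihood ratio figures are by exact enumeration of all outcomes.

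| Evaluable per arm | Continuity-corrected | Fisher | Uncorrected | Likelihood ratio |
|---|---|---|---|---|
| 50 (SAP 6 plan after 15% loss) | 81.5% | 82.9% | 86.6% | 87.6% |
| 40 (assumed) | 70.4% | 72.5% | 78.0% | 79.7% |
| 30 (SAP 5 count at closure, even split) | 54.8% | 56.1% | 65.3% | 66.5% |

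The likelihood ratio figure at 30 per arm is slightly flattered: its true type I error there is 5.2% to 5.8% for underlying rates of 0.3 to 0.7.

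**Step 4: detectable difference at 30 per arm.** With placebo at 40%, the difference detectable with 80% power is 34.8 points (likelihood ratio), 35.1 (uncorrected) or 38.1 (continuity-corrected), against the 30 points planned.

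**Step 5: should 15% also come off the 60?** No. SAP 5 counts patients who have already been dosed up to Day 10. The primary endpoint uses Days 1 to 10 (SAP 7.3.3), and beyond randomization and dosing the modified ITT population asks only that a patient "had at least one GSRS score measurement during the Day 1 - Day 10 period" (SAP 7.1.1). These patients have passed the window in which discontinuation could remove them.

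**Step 6: is 60 the final number?** Not necessarily. SAP 5 follows patients already enrolled, protocol 9.1 counts a subject as enrolled from consent, and the modified ITT population takes any randomized and dosed patient with one score in the window. Together these allow subjects in screening or DMF monitoring at closure to be dosed and analysed later, but the SAP gives no count of them. The 40-per-arm row is therefore an illustration.

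**The case against.** The best defence is that nothing is hidden or miscalculated. SAP 5 announces the closure in the section just before SAP 6. SAP 6 is conditional: it says what 118 would provide, and that remains true. SAP 1 says that the SAP is based on protocol Version 3, which explains why the size text was carried over. The stop is administrative, and the profile-likelihood 95% confidence interval in SAP 7.3.3 will show the precision achieved. Recalculated power would use planning assumptions only, so trial results could not affect it.

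Much of this stands. SAP 6 contains no arithmetic error, and a reader who might infer one from the mismatch would be wrong. The consequence is limited to what is on record. But disclosure in SAP 5 does not correct SAP 3.1, which still states 118 as what is expected, and it does not supply the missing power. An interval reported afterwards does not replace a planning figure.

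A reader might also infer a drop from about 80% to 45% to 62% by taking the SAP's 15% loss off 30 per arm. The documents do not support that. It deducts loss from patients already dosed to Day 10. It also sets one method's starting figure against a range over four methods; the matching start at 50 per arm is 81.5% to 87.6%.

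Nor do the documents show that the final analysis will have only 60 patients. At an assumed 40 per arm, the uncorrected and likelihood ratio methods come close to 80%.

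**Conclusion.** The point holds as an unreconciled sample size with a missing power figure. If about 30 per arm are evaluable, power for the SAP's own 30-point effect is about 55% by the formula that reproduces 118, and 55% to 67% across the four methods, where the same methods give 81.5% to 87.6% at 50 per arm.

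This rests on 40% against 70%, two-sided 5%, an even split, Day 10 data for all 60, and an unadjusted, unweighted test. The even split is not assured, because randomization precedes the symptom threshold that triggers dosing. The planned primary model is weighted and covariate-adjusted, so its power could differ somewhat. The number at closure is approximate and may be added to; the true final power cannot be fixed until the SAP states the expected number. It should be corrected, but it does not undermine the analysis plan itself.

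**What to change.** In SAP 3.1 (Study Overview) and SAP 6, label 118 dosed and about 80% power as the original target, and refer to the closure in SAP 5. State the expected final number dosed and analysed, and say whether subjects in screening or DMF monitoring at closure will be dosed and included. Restate power and detectable difference for that number, naming the test and showing the loss assumption, with any loss applied only to patients who have not yet reached Day 10. As an illustration only, 30 evaluable per arm would read: 55% to 67% power for 40% against 70%, and 35 to 38 points detectable with 80% power.

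The cost is a few sentences and one recalculation. No patient is added, and no test, population or endpoint changes. The downside is that the power on record becomes less favourable.
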